## 13.1.1.3. Indoor environment monitoring of households

In the selected households the indoor environment monitoring sensors will be installed by suitably trained research assistants during, or within 2 days of, the first IDI. The specific sensor and installation thereof is described in Table 2 below.

Table 5: Sensor that will be installed in the household, detailing position of installation

Measure	Sensor	Installation position
Drybulb Temperature (DT)	Onset Hobo MX1101	Installed on the Southern
		and Northern wall
Relative Humidity (RH)		between 1000 -1800mm
		affl.
		Sensors to be installed
		out of direct sunlight.

Drybulb temperature and relative humidity measures will be continuously monitored in the households using an ONSET HOBO MX1101 sensor. The sensors continuously monitor the indoor temperature at 15-minute intervals and store the data on the onboard memory. The sensors are battery powered and have an accuracy of  $\pm 0.21^{\circ}$ C from 0° to 50°C for temperatures and  $\pm 2\%$  from 20% to 80% for relative humidity. The sensor displays the room temperature and humidity so this can be seen by household members should they be

interested. They will not make any sounds, unless programmed to warn residents of temperature thresholds being crossed – this feature will be disabled to reduce disturbance to household members.

The sensor will be installed using a temporary wire bracket that is hooked to the top of the existing corrugated iron walls of the household. For households with brick walls, the installation of bracket will be adjusted so as not to damage the wall. The house wall will not be damaged in any way and the bracket will be adjusted to the specific conditions. A single sensor will be installed in the bedroom/sleeping area (of the research participant) or lounge of each household; depending on the preference of the participant and household head. The research assistant will confirm the position of the sensor with the homeowner and research participant prior to installation. The selected sensors will not disrupt the research participants visually nor will they emit any sounds.

Data will be collected from the indoor household sensors monthly, using a bluetooth enabled data download application on a mobile device or computer. Homeowners will be informed well in advance about the data collection date and their availability will be confirmed.

Research assistants will not enter a home unaccompanied by the homeowner or research participant and will also visit the households to download the data in groups of two.

The sensors have a downloading range of 30m (line of sight), so the research assistants will be required to enter the homes to download the data. The data download will take a maximum of 60 seconds per sensor, researchers should not spend more than 5 minutes at a household to download the data. The temperature data will be linked to a predetermined sensor number. The downloaded data will then be uploaded to a secure central digital repository housed at CeSHHAR. See section 9 for the data handling, storage and data management protocol.

## 14. CO-DESIGN WORKSHOPS

## 14.1.1. Study Design

We propose up to 60 participants in total constituted by pregnant and postpartum women, household heads, community leaders, health workers, health facility managers, sub-national and national stakeholders. We believe this sample size of n=60 will allow for inclusivity and diversity of perspectives to ensure that the refined intervention package address multiple dimensions of the issue. By fostering collaboration and a shared understanding of heat-related challenges, stakeholders will generate context-specific solutions tailored to the unique needs of each intervention level and component. Through active knowledge exchange and the blending of cross-disciplinary insights, these workshops promote innovative and practical strategies for enhancing resilience to heat across all levels of society.

# 14.1.2. Participant Sampling

We will invite participants including pregnant and postpartum women, household heads, community leaders, health workers and health officials at subnational and national level to participate in a co-design workshop to discuss and refine interventions that have been implemented. Potential participants will be approached individually or in groups, where possible, and the study will be explained to them. Those who express interest in joining the co-design workshop will have the informed consent form read to them and the form will be signed on the day of the workshop (Appendix 30). This information sheet will include information on the co-design process that will take place and the participants role in this process. The detailed informed consent process is described in Section 31.

— IndividualHousehold Level: At the household level, we will invite women and household heads who participated in AR1 and AR2 to the codesign workshop to provide input on the ongoing interventions implemented in AR1 and AR2 for further refinement. To ensure a rich diversity of perspectives, we will ensure to have representation from people of diverse socio-economic status, ethnic background, and age. Women and household heads will be separated into two groups to manage and minimise power dynamics.

- Community level: We will invite a subset of community leaders who participated in the
  first co-design workshop to also provide input on all of the selected interventions also for
  the refinement of the implemented interventions.
- Health systems and policy Level: We will invite a sub-set of health officials and other stakeholders who also participated in the first co-design workshop, including health workers, district health officers, local and national government officials, and representatives from local non-governmental organizations (NGOs). We will ensure that all geographical areas represented by our study sites are included, thereby capturing the heterogeneity of the region.

All results will be categorised and incorporated into a framework and summarised in a table similar to Table below.

Proposed Framework of themes and results from optimisation of the intervention

Domain	Heat Adaptation interventions identified						
	Behaviour	Health	Modifications	Nature	Policy	Poverty	
	changes	systems	to the built	based	action	reduction and	
	and	and	environment	interve		equity	
	awareness	services		ntions			
Individual							
(pregnant and							
postpartum							
women and their							
newborns)							
Health workers							
Household							
Community							
& Health Facility							
Health systems							
Policy and outside							
environment							

(subnational and			
national levels)			

#### 15. COST CONSEQUENCE ANALYSIS

The cost-consequence modelling will assess the economic feasibility of implementing the multi-level and multicomponent community-led heat adaptation and mitigation interventions in Zimbabwe. This modelling aims to capture both direct financial costs (expenditure on goods, services, and volunteer time) and non-financial costs (donated goods or volunteer time).

# 15.1.1. Prospective costing study

The prospective nature of HAPI provides an opportunity for us to examine costs over time as it is not limited by the short nature of most studies. This will allow us to track changes in the cost structure over time, examining the variation as the interventions evolve. We will assess the cost implications of rolling out the intervention in the community and monitor the evolution of the programme.

- i) Specifically, we will assess:
  - a. the changing cost structure of heat adaptation and mitigation with intervention roll-out.
  - b. Cost variation with programme evolution and scale.

# 15.1.2. Top down costing approach.

This approach will utilise comprehensive data (e.g., expenditures, time sheets, M&E reports) to allocate intervention expenditures to sites and then to activities. The costs will be categorised by activity and input type, focusing on capturing total costs, especially start-up and recurrent capital expenditures, and applying a 3% annual discount rate. Specifically, we will assess:

a. Comprehensive access to data (expenditures, time sheets, M&E etc) to facilitate allocation of intervention expenditures to sites and then to activities

- b. Costs will be disaggregated and categorised by activities and input type.
  - i. Start-up capital and recurrent costs
- c. Approach captures total cost better though less precise for disaggregating costs at the activity level.
- d. First allocating out specific expenditures that could be clearly tracked to sites, then by M&E outputs such as training, persons reached, distances etc
- e. All expenses prior to AR1 will be treated as start-up costs and together with capital costs annualised at 3% discount rate

# 15.1.3. Bottom up costing

Supplementing the top-down approach, a more granular bottom-up cost analysis will be conducted, particularly at the site level. A bottom up approach will supplement costing (more site level data collection) to ensure robustness of cost allocation. This will include formative baseline assessments in HAPI and HH in three sites, interviews with HCWs, stakeholders, and researchers, and time-motion studies to observe the cost allocation in real-time. Specifically, we will assess:

- a. Formative baseline in HAPI and HH in 3 sites
- b. Includes interviews with HCW, Stakeholders, Research staff, Stakeholders listed in AR1 and AR2 interview guides above
- c. Time and motion analysis

## 15.1.4. Cost data analysis

All data from these processes will be entered and analysed using Microsoft Excel to ensure accurate data interpretation and reporting.

Our approach helps to determine the true economic impact and sustainability of the interventions, ensuring that the financial, human, and material resources are appropriately accounted for. The study will then inform decisions on scaling the intervention in other areas. In terms of the timeline and methods, we aim to complete the process efficiently within stage 2 of implementation. This approach guarantees that the economic analysis is directly tied to the operational needs and the scaling potential of the heat adaptation strategies

#### **16. STUDY-RELATED FORMS**

Forms that will be used in the implementation of the evaluation include:

- Pre-intervention cohort: Participant Information sheet and informed consent form (Appendix 22)
- Post-intervention cohort: Participant Information sheet and informed consent form (Appendix 23)
- AR1: Household head telephonic permission (Appendix 24)
- AR1: Household head written consent (Appendix 25)
- AR1: Participant Information sheet and informed consent form (Appendix 26)
- AR2: Household head telephonic permission (Appendix 27)
- AR2: Household head written consent (Appendix 28)
- AR2: Participant Information sheet and informed consent form (Appendix 29)
- Co-Design: Participant Information sheet and informed consent form (Appendix 30)
- Pre- and post-intervention cohort: Baseline Questionnaire (Appendix 31)
- Pre- and post-intervention cohort: Follow-up Questionnaire (Appendix 32)
- Pre- and post-intervention cohort: Postpartum Questionnaire (Appendix 33)
- AR1 and AR2: Questionnaire (Appendix 34)
- ARI and AR2: Context Tracker (Appendix 35)
- AR1 and AR2: Monthly Researcher journal (Appendix 36)
- AR1 and AR2: Microsoft Excel costing spreadsheet (Appendix 37)
- AR2: Field perspectives IDI guide (Appendix 38)
- AR2: Field perspectives KII guide (Appendix 39)
- AR2: Field perspectives FGD guide (Appendix 40)

# 17. QUALITY CONTROL AND QUALITY ASSURANCE

All staff involved in data collection will receive thorough training on the data collection methods and procedures that they will be involved in. This will help to ensure that interviews are conducted consistently, and temperature monitoring data are collected consistently and accurately at all times.

Various administrative forms will be used to track the collection of data and ensure timely follow-up with the participants and scheduling of interviews (e.g. Recruitment and Enrolment logs; Data tracking log).

#### 18. DATA HANDLING AND ANALYSIS

## 18.1.1. Data Entry, Editing and Management

The data collected will be directly uploaded to the central REDCap database housed at CeSHHAR and may also be shared with Wits RHI. This will ensure that post editing will be limited as well as traceable. A log of all electronic database corrections will be retained via the REDCap database manager.

#### 18.1.2. Data Analysis

Evaluation of complex interventions involves consideration of a wide range of outcomes. For purposes of sample size, the primary pilot-effectiveness outcome is mild-moderate hypovolemic maternal dehydration during labour (urine specific gravity >1.015, measured by handheld optical refractometer, Sper Scientific portable clinical refractometer 300005). This reflects hydration practices, and heat exposure (fluid loss through perspiration). Secondary outcomes include process indicators for interventions, heat strain, mental wellbeing, composite maternal-clinical outcomes (obstetric emergencies, emergency Caesarean section, pre-eclampsia/eclampsia, antepartum or postpartum haemorrhage, and sepsis) and composite infant clinical-outcomes (preterm birth, low birth weight, APGAR score ≤6, and neonatal admission). Household temperatures will be used to determine effectiveness of household level interventions.

Baseline survey data will be analysed descriptively using percentages and presented in tables and will be included in reports and publications as such. Survey baseline and follow-up data will be compared using Student's t test, Mann-Whitney U test and chi-square, as applicable. Analyses will be presented overall, and by site, facility, and pre-specified population subgroups (to identify high-risk groups). Binomial multivariable regression will compute risk differences between pre- and post-measures in the primary outcome, controlling for multihazard factors and changes in climate exposures over time, with fixed-effect clusters. If size or direction of effectiveness differs markedly between facilities, or sites then analysis may be restricted to facility- or site-level.

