### 4. PROTOCOL SUMMARY

Temperatures in Southern Africa are rising twice as fast as the global average, posing significant health risks for maternal and newborn health. Sub-Saharan Africa faces additional challenges due to poverty, inadequate infrastructure, and ecosystem degradation, making vulnerable groups, such as pregnant women in subsistence-farming communities and urban informal settlements, less able to adapt. Social norms and gender inequalities further constrain women's agency and ability to cope with these changes. Studies globally show that heat can lead to adverse outcomes for maternal and neonatal health, including preterm birth, stillbirth, and low birth weight. However, research on heat-related harms in pregnancy in Africa is limited, especially around interventions to reduce these harms. Addressing heat stress requires complex and multi-level solutions, as simple interventions may not be sufficient. Accurate measurement of temperature exposure is essential for understanding health impacts, and this study will employ innovative methods, such as temperature measurements in healthcare facilities and households, to address exposure misclassification. Moreover, little is known about women's perceptions of heat during pregnancy and their current adaptive strategies, despite a growing body of evidence on its adverse health effects.

To develop effective interventions, it's crucial to understand the impacts of heat stress and how individuals and communities respond to it. To understand this complex interplay, we will employ a 2 staged design process-Stage 1 Development of an intervention package and Stage 2 Feasibility testing, intervention optimisation and theory-based evaluation. Stage 2 is preceded by a co-design process involving stakeholders to develop the intervention for testing. This summary outlines the activities conducted in Stage 1, the co-design process, and Stage 2, all of which are integral components of the broader HAPI project (Heat Adaptation for Pregnant Women and Infants).

The overall aim of the HAPI study is to develop co-produced multi-level, multi-component interventions to reduce heat impacts on maternal and newborn health (MNH) in diverse contexts.

The primary objectives of the study are:

- To observe and document the experiences and responses of pregnant women to heat in antenatal clinics and the first stage of labour in maternity settings.

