### 11.1.5. Sample Size

For the purposes of determining the required sample size, the primary pilot-effectiveness outcome is mild-moderate hypovolemic maternal dehydration during labour (urine specific gravity >1.015, measured by handheld optical refractometer, Sper Scientific portable clinical refractometer 300005 or similar). This reflects both hydration practices, and heat exposure (fluid loss through perspiration). We calculated the sample size to provide sufficient power for country-specific analyses; a pooling across countries may not be possible due to heterogeneity in intervention package and effectiveness. With about 800 women and 15% attrition, we will have >95% power to detect a 15% difference in the proportion of women with primary outcome between the pre- and post-intervention cohorts. In the before cohort, based on a literature review, we estimated 30-60% of women will have mild-moderate dehydration during labour (level varying by ambient temperature and season).

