- Clinical outcomes in newborns (composite)^			х			х			
Biological urine sample									
- Urine specific gravity assessment (primary outcome)	х	х	х	х	х	х			

- Maternal composite clinical outcomes: 1 or more of the following obstetric emergencies, emergency Caesarean section, preeclampsia/eclampsia, antepartum or postpartum haemorrhage, sepsis.
- Newborn composite clinical outcomes, 1 or more of the following: stillbirth, preterm birth, low birth weight, APGAR score ≤6, neonatal admission

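### The newborn composite counts stillbirth in the Figure 5 footnote but not in section 18.1.2, so some stillbirths could be scored as event-free or dropped

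*Protocol*

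**What the plan says.** The Figure 5 footnote in section 11.1.9 gives both a component list and a scoring rule: "Newborn composite clinical outcomes, 1 or more of the following: stillbirth, preterm birth, low birth weight, APGAR score ≤6, neonatal admission".

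Section 18.1.2, in its account of the secondary outcomes, gives "composite infant clinical-outcomes (preterm birth, low birth weight, APGAR score ≤6, and neonatal admission". Stillbirth is absent and there is no scoring rule.

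Both are current text for the same pre-post study. The schedule rows in Figure 5 and Table 1 name the newborn composite but do not define it further. The Protocol Summary (section 4) cites stillbirth among the harms that motivate the work: "heat can lead to adverse outcomes for maternal and neonatal health, including preterm birth, stillbirth, and low birth weight".

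**The concern.** A composite outcome needs one component list. Here an analyst could follow either list, and the two can classify the same infant differently. The infant at issue is a stillbirth, which section 4 names among the harms linked to heat. Under the section 18.1.2 list, some fetal deaths would be counted with the healthy births or would leave the analysis. With two lists on file, the choice between them could also be made after the data are seen.

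**Working it through.** **Side-by-side comparison**

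| Component | Figure 5 footnote | Section 18.1.2 |
|---|---|---|
| Stillbirth | yes | no |
| Preterm birth | yes | yes |
| Low birth weight | yes | yes |
| APGAR score ≤6 | yes | yes |
| Neonatal admission | yes | yes |
| Scoring rule | one or more | none given |

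The four shared items appear in the same order. The maternal composite serves as a control: its components in the footnote ("emergency Caesarean section, preeclampsia/eclampsia, antepartum or postpartum haemorrhage, sepsis", with obstetric emergencies) agree with those in section 18.1.2. Only the newborn list differs.

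**How a stillbirth is classified**

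- Footnote list: always an event.
- Section 18.1.2 list, stillbirth preterm or of low birth weight: an event, because neither component is restricted to live births.
- Section 18.1.2 list, term and normal weight, APGAR of 0 recorded: an event.
- Section 18.1.2 list, term and normal weight, no APGAR recorded: not an event, since a stillborn infant is not admitted to neonatal care. It is event-free, or missing if an unrecorded APGAR removes the infant.

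Only the last group changes status.

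**Size**

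The protocol states no figure for this outcome, so there is none to reproduce. Inputs:

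- 400 women per cohort and 15% attrition (section 11.1.5): 400 × 0.85 = 340, taken as about one birth per woman.
- Stillbirth risk of 1-3%: an assumption, not in the protocol.
- Share of stillbirths meeting none of the four listed components, 10-50%: also an assumption.

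Results:

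- Stillbirths per cohort: 340 × 0.01 = 3.4, to 340 × 0.03 = 10.2. This is the upper bound on those reclassified.
- Reclassified per cohort: 340 × 0.01 × 0.10 = 0.34, to 340 × 0.03 × 0.50 = 5.1. In percentage points: 0.1 to 1.5.
- One infant scored event-free instead of as an event: 1/340 = 0.29 points.
- One infant dropped instead, with k other events in the cohort: (k+1)/340 − k/339 = (339 − k)/(340 × 339), which is at most 1/340.

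**Primary outcome**

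The power statement in section 11.1.5 concerns dehydration in labour only: "With about 800 women and 15% attrition, we will have >95% power to detect a 15% difference in the proportion of women with primary outcome". With 340 per cohort and an assumed two-sided 5% level, power for a 15-point reduction is 99.7% from a pre-intervention rate of 30%, 97.8% from 50% and 97.6% from 60%. The stated figure reproduces and does not depend on the newborn composite.

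**The case against.** The strongest reply is that section 18.1.2 does not displace the footnote. It is a prose list with no scoring rule, and its regression model is stated for the primary outcome. An analyst who needs a scoring rule finds it only in the footnote, which counts stillbirth. This stands in part: the protocol does not fix the wrong scoring, it leaves two lists. But section 18.1.2 is the section on data analysis, and nothing says that the footnote prevails.

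A second reply is that a composite limited to live births, with stillbirth reported alongside, would be coherent. It would, but neither place states that restriction, and the footnote contradicts it.

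Three stronger readings are tempting, and the protocol does not support them:

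- A reader might infer that every stillbirth is lost under section 18.1.2. Those that are preterm, of low birth weight or given a low APGAR score still count on a plain reading.
- A reader might infer that more stillbirths would lower the composite. That needs the extra stillbirths to fall in the narrow unscored group and those infants otherwise to have had an event. Nothing in the protocol shows this.
- A reader might infer that the trial's main result is at risk. The composite is one of several secondary outcomes.

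**Conclusion.** The contradiction is real, and it does not depend on any assumed rate. Its consequence is limited. Only stillbirths at term, of normal weight and without a recorded APGAR change status, and each moves a cohort's composite by about 0.3 points at most. The 3 to 10 stillbirths per cohort are an upper bound resting on an assumed 1-3% risk. Under the further assumption that 10-50% of them meet no listed component, the shift is 0.1 to 1.5 points within a cohort. The pre-post comparison is distorted only by the difference between the cohorts in that shift, and its direction cannot be foreseen. This should be corrected because the two definitions can give different results for a clinically important secondary outcome. It does not threaten the study's main conclusion.

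**What to change.** In section 18.1.2, add stillbirth to the infant composite so that the components match the Figure 5 footnote, and repeat the footnote's one-or-more rule. Add one sentence: the composite is scored over all births, live and still, and a stillbirth counts as an event whether or not an APGAR score was recorded. Reporting stillbirth separately as well is optional.

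The cost is one word and one sentence. Figure 5 already places the newborn composite, defined there with stillbirth, under the pregnancy and birth records, so no new data collection is implied and the sample size does not change.

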### 11.1.6. Participant sampling

*Pre- and post-intervention cohorts*: Consecutive eligible women in Mt Darwin District health facilities will be approached for recruitment. Consecutive recruitment minimises selection biases. We will enrol at least 5-10 women per day, with each cohort including up to 400 women (up to 400 pre-intervention and up to 400 post-intervention). Duration of total planned follow up time is about 2-4 months for each woman, assuming that most women complete pregnancy at around 40 weeks gestation. Routine clinical follow-up visits at antenatal clinic are generally at 20-, 26-, 30-, 34-, 36-, 38-, and 40-weeks during pregnancy (+/- 7 days), then during the first stage of labor, and again postpartum within 72 hours postpartum (window closes 10 days after delivery). Pre- and post-intervention cohort recruitment is spaced around 9-12 months apart and timed to coincide with the hot season.

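### The only model tied to the primary outcome cuts labour urine specific gravity at 1.015; the overall test keeps its power, but facility and subgroup comparisons lose power that the numeric reading could recover

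*Protocol*

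**What the plan says.** Section 11.1.5 sizes the study on "mild-moderate hypovolemic maternal dehydration during labour (urine specific gravity >1.015" and section 18.1.2 repeats the definition: "urine specific gravity >1.015, measured by handheld optical refractometer, Sper Scientific portable clinical refractometer 300005". In both places the outcome is primary for the purpose of sample size ("For purposes of sample size, the primary pilot-effectiveness outcome is mild-moderate hypovolemic maternal dehydration during labour").

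The power claim is "With about 800 women and 15% attrition, we will have >95% power to detect a 15% difference in the proportion of women with primary outcome", and for the pre-intervention cohort "we estimated 30-60% of women will have mild-moderate dehydration during labour". Section 11.1.6 plans equal cohorts, "with each cohort including up to 400 women (up to 400 pre-intervention and up to 400 post-intervention".

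For the analysis, section 18.1.2 states: "Binomial multivariable regression will compute risk differences between pre- and post-measures in the primary outcome", adjusted for hazard and climate covariates with fixed effects for clusters. It adds: "Analyses will be presented overall, and by site, facility, and pre-specified population subgroups (to identify high-risk groups". It also allows the analysis to be confined to single facilities or sites if effects diverge clearly between them. A t test and a Mann-Whitney test are named for survey data, without mention of USG. Section 12.1.2 names three facilities for the facility-level interventions, and section 7 lets Stage 2 data collection extend to others.

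**The concern.** Cutting a numeric measurement at one point treats all readings above 1.015 as equal and all readings at or below it as equal. A difference between the cohorts that lies wholly on one side of the cut does not enter the analysis, and a shift of the whole distribution is estimated less precisely than the data allow.

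With 400 women per cohort the overall test can absorb this. A single facility or subgroup may hold a third of the women or fewer. The plan uses those comparisons to find high-risk groups and to decide whether to report by facility, so a real effect there could be missed although the readings already taken would have shown it.

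**Working it through.** **Inputs from the protocol.** 400 women per cohort, 15% attrition, a baseline of 30-60% and a 15-point difference. After attrition, 400 × 0.85 = 340 per cohort.

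**Assumptions, because the protocol is silent.** Two-sided alpha 0.05; independent women; a fall of 15 points; USG roughly normal with equal SD and a uniform shift; facility shares either equal thirds (340 / 3 ≈ 113) or, as an illustration, 50/30/20 (170, 102 and 68 per cohort).

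**Formulas.**
- Binary power: Φ{(|p1 − p2| − 1.96 × SE0) / SE1}, with SE0 = √[2p̄(1 − p̄)/n] and SE1 = √[(p1(1 − p1) + p2(1 − p2))/n].
- Continuous power: two-sample t test (noncentral t), with the standardised shift that produces the same fall, d = z(p1) − z(p2). This gives d = 0.512 (30 to 15%), 0.399 (45 to 30%) and 0.379 (60 to 45%).

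**Step 1: the plan's own figure.** For 60 to 45% at n = 340, SE0 = 0.0383 and SE1 = 0.0379, so (0.15 − 0.0751)/0.0379 = 1.98 and power is 97.6%. For 30 to 15%, SE0 = 0.0320 and SE1 = 0.0315, which gives 2.77 and 99.7%. The claim of over 95% is reproduced.

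**Step 2: one facility of three.** For 45 to 30% at n = 113, SE0 = 0.0644 and SE1 = 0.0636, so (0.15 − 0.1262)/0.0636 = 0.373 and binary power is 64.6%. On the numeric scale the noncentrality is 0.399 × √(113/2) = 3.00 and power is 84.7%.

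**Step 3: across stratum sizes** (power in %, binary v continuous; gains from unrounded values):

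| Per cohort | 30 to 15% | 45 to 30% | 60 to 45% | Gain, points |
|---|---|---|---|---|
| 340 (overall) | 99.7 v 100.0 | 98.2 v 99.9 | 97.6 v 99.9 | 0.3-2.2 |
| 170 | 91.5 v 99.7 | 81.8 v 95.6 | 79.4 v 93.6 | 8-14 |
| 113 | 77.4 v 96.9 | 64.6 v 84.7 | 61.8 v 81.0 | 19-20 |
| 102 | 73.1 v 95.3 | 60.1 v 80.9 | 57.4 v 76.8 | 19-22 |
| 68 | 55.4 v 84.2 | 43.8 v 63.6 | 41.6 v 59.3 | 18-29 |

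At 113 per cohort the gain reaches 21 points for baselines of 35-40%.

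**Step 4: skewed readings.** Simulation at 113 per cohort (2,000 runs per baseline; right-skewed gamma USG of shape 2; effect as a change of scale; readings rounded to 0.001) gave, for baselines of 30, 45 and 60%: binary 77.8, 64.3 and 64.8%; t test 93.4, 84.0 and 86.6%; Mann-Whitney 88.8, 76.6 and 80.6%. The gains are 16-22 points (t test) and 11-16 points (Mann-Whitney).

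**Step 5: cohort-by-facility interaction.** Take two facilities of 113 per cohort, one with the 15-point effect and one with none. The binary SE is √[(3p1(1 − p1) + p2(1 − p2))/113] and the continuous SE is √(4/113) in SD units. Power is 37-45% binary and 52-78% continuous: better, but below 80% throughout.

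**The case against.** The strongest objection is that nothing is wrong with the primary test. It keeps its stated power, the numeric scale adds at most 2.2 points overall, and facility and subgroup results are only to be presented, in a pilot-effectiveness study, with no power promised for them. All of that stands. A reader might infer that the sample size fails or that a power commitment is broken; neither is so.

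Second, a supporting model could sit in a statistical analysis plan that is not shown, and the t and Mann-Whitney tests named for survey data might be meant to cover USG, which is measured at the same visits. The text does not exclude this. It is therefore safe to say only that no numeric-scale model is tied to the primary outcome, not that none will be run. Nor does the protocol say that numeric readings will go unrecorded.

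Third, the gain rests on a shift across the whole distribution. In an extreme simulation at 113 per cohort, where only women just above the cut fell to just below it, binary power was 63-78% and t-test power about 6%. That case is illustrative rather than expected, but it shows that the advantage can reverse.

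Fourth, it is tempting to describe a woman moving across the cut, or improving without crossing it. Section 11.1.4 excludes pre-intervention women from the post-intervention cohort, so the primary contrast is between different women. What the cut hides is a difference in distribution between cohorts, not change within a woman.

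**Conclusion.** The point holds as a modest, inexpensive improvement. The stated analysis uses only the side of 1.015 on which a reading falls. Overall this costs almost nothing. In strata of about one third of the sample, binary power for a 15-point difference is 62-77%, against 81-97% on the numeric scale.

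No single figure for the loss should be quoted without its conditions. The 19-20 points belongs to three equal facilities, roughly normal USG, a uniform shift and alpha 0.05. Across the stratum sizes examined the range is about 8-29 points, and with skewed USG at 113 per cohort about 11-22. The documents give neither facility shares nor the distribution of USG.

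**What to change.** In section 18.1.2:

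- Keep the risk difference for USG above 1.015 as the headline result, so that the clinical label and the sample-size statement stand.
- Prespecify, as a supporting analysis, a linear regression of labour USG on its recorded scale with the same covariates, facility fixed effects and robust standard errors.
- Use that model alongside the proportions above 1.015 for the facility and subgroup comparisons and for the cohort-by-facility interaction, and state that the interaction may still be underpowered.
- Require the numeric reading, not only the category, to be stored.

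The cost is a few sentences and one extra model, with no added women, visits or measurements. The downside is that a mean difference in USG is less direct clinically than a proportion dehydrated, which is why the proportion stays as the headline.
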